4. ELIGIBILITY ASSESSMENT

All subjects age 2 and older with SAA who have not received prior ATG-based immunosuppressive therapy and lack a suitable matched sibling marrow donor, or are not allogeneic transplantation candidates due to patient choice, advanced age, or infeasibility of transplantation will be considered for enrollment.

Eligibility will be determined on another National Heart Lung and Blood Institute (NHLBI) screening protocol (97-H-0041) or any other active Hematology branch protocol. The time between determination of eligibility and signing consent to participate on this protocol and initiate treatment on this protocol will not exceed 90 days. Due to the nature of SAA, counts may fluctuate depending on transfusions. Because of this, the lowest clinical laboratory result (ANC, platelet, and/or absolute reticulocyte count) obtained within 60-days prior to treatment initiation will be used for eligibility determination.

4.1 Inclusion Criteria

- 4.1.1 Severe aplastic anemia characterized by
Bone marrow cellularity <30% (excluding lymphocytes) *

AND

At least two of the following:

- Absolute neutrophil count < 500/ μ L
- Platelet count < 20,000/ μ L
- Absolute reticulocyte count < 60,000/ μ L

- 4.1.2 Age \geq 2 years old

- 4.1.3 Weight > 12 kg

*If a range is provided instead of the overall bone marrow cellularity the median value of that range will be used for this inclusion criterion.

4.2 Exclusion Criteria

- 4.2.1 Known diagnosis of Fanconi anemia
- 4.2.2 Evidence of a clonal disorder on cytogenetics performed within 12 weeks of study entry.
Patients with super severe neutropenia (ANC < 200 / μ L) will not be excluded initially if cytogenetics are not available or pending. If evidence of a clonal disorder consistent with myelodysplasia is later identified, the patient will go off study – see section 9.6
- 4.2.3 Prior immunosuppressive therapy with any ATG, alemtuzumab, or high dose cyclophosphamide
- 4.2.4 SGOT or SGPT > 5 times the upper limit of normal
- 4.2.5 Subjects with known liver cirrhosis in severity that would preclude tolerability of cyclosporine and eltrombopag as evidenced by albumin < 35g/L
- 4.2.6 Hypersensitivity to eltrombopag or its components
- 4.2.7 Infection not adequately responding to appropriate therapy

- 4.2.8 Moribund status or concurrent hepatic, renal, cardiac, neurologic, pulmonary, infectious, or metabolic disease of such severity that it would preclude the patient's ability to tolerate protocol therapy, or that death within 7-10 days is likely
- 4.2.9 Potential subjects with cancer who are on active chemotherapeutic treatment or who take drugs with hematological effects will not be eligible
- 4.2.10 Current pregnancy, or unwillingness to take oral contraceptives or use a barrier method of birth control or practice abstinence to refrain from pregnancy if of childbearing potential during the course of this study
- 4.2.11 Inability to understand the investigational nature of the study or to give informed consent or does not have a legally authorized representative or surrogate that can provide informed consent per section 11.6.

5. TREATMENT PLAN

5.1 Horse Anti-thymocyte Globulin (h-ATG) Administration

A single treatment course of h-ATG will be administered at a dose of 40 mg/kg/day for 4 consecutive days. Dose will be calculated based on actual body weight. H-ATG will be infused intravenously for approximately 4 hours. The infusion time may vary based on the patient and circumstances. Infusion times may be extended up to 24 hours to improve tolerance of infusional side effects such as fever, chills and hypotension if necessary. Serum sickness prophylaxis with oral prednisone (or intravenous methylprednisolone as clinically indicated) at 1 mg/kg/d will begin prior to the first dose of h-ATG, and will be continued for 10 days total and then tapered over the subsequent 7-14 days. Those subjects who develop serum sickness may require a longer tapering schedule and will be dosed individually as clinically indicated.

5.2 Cyclosporine (CsA)

Day 1 to Month 6 dosing:

For subjects \geq 12 years of age, cyclosporine will be started on day 1 at 3 mg/kg/dose by mouth administered every 12 hours (total daily dose of 6 mg/kg/day). Dosing will be based on actual body weight except in obese subjects. For obese subjects (defined as a body mass index > 35 in adult subjects [> 20 years of age] and > 95 th percentile in subjects 12 to 20 years of age), cyclosporine dosage will be based on an adjusted body weight that is calculated as the midpoint between the ideal body weight and actual body weight (see below for definition of ideal body weight).

For subjects $<$ 12 years of age, cyclosporine will be started on day 1 at 6 mg/kg/dose by mouth administered every 12 hours (total daily dose of 12 mg/kg/day). Dosing will be based on actual body weight except in obese subjects. For obese subjects (defined as a body mass index > 95 th percentile in subjects 12 to 20 years of age), cyclosporine dosage will be based on an adjusted body weight that is calculated as the midpoint between the ideal body weight and actual body weight (see below for definition of ideal body weight).

Cyclosporine dosing will be adjusted, at the investigator's discretion, to aim for a therapeutic trough level between 200 and 400 mcg/L. In subjects who had a therapeutic CsA level established prior to protocol enrollment, the same CsA dose will be initiated with the h-ATG and adjusted accordingly. Cyclosporine dose may be interrupted or adjusted as clinically indicated at the discretion of the investigator for side effects. Interruptions will only be recorded in the medical record.

In between NIH landmark visits, only CsA levels will be tracked and recorded into the clinical database.

Ideal Body Weight Definitions:

Ideal body weight (adult male, age > 20): 50 kg + 2.3 kg per inch over 5 feet

Ideal body weight (adult female, age > 20): 45.5 kg + 2.3 kg per inch over 5 feet

Ideal body weight (pediatrics, ages 2–20): 50th percentile weight based on CDC growth curves.

Month 6 to Month 24 cyclosporine dosing:

On review of the data as of September 17, 2014 where a trend towards a higher than expected number of relapses after the 6 month landmark visit were observed and salvaged by resuming cyclosporine, the protocol was amended to prolong administration of cyclosporine beyond 6 months per the following:

At the 6-month landmark visit, responders will have the CsA dose reduced to 2.0mg/kg/day administered orally at a fixed dose through the 24 month timepoint. Previous anecdotal experience suggested that a gradual taper of CsA may avoid relapse, but when we adopted this strategy prospectively in our clinical trials (03-H-0193 and 06-H-0034) the rate of relapse was unchanged (Scheinberg, Rios, et al. AJH 2014⁶⁷). However, time to relapse was delayed by 1 year with the longer course of CsA and may be dose-dependent. The CsA dose at the time of relapse during the taper phase was at a median of 1.32 (range: 0.52-4.18) mg/kg/day and a mean of 1.8 mg/kg/day. This suggests that a CsA dose level above these levels might preclude relapse and improve tolerability of chronic maintenance. For remaining subjects due for the 6 month timepoint on cohort 2 we will prolong administration of cyclosporine beyond 6 months. CsA will continue to be administered from Day 1 to 6 months, but from 6 months to 2 years CsA will be administered at a lower fixed daily dose (2 mg/kg/day) in an attempt to improve relapse, a secondary endpoint, among responders in the study.

Medication dosing errors, dose delays or dosing interruptions:

Interruptions such as delays in request for medication refills or medication errors by subjects will be recorded in the medical record.

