6.2 On Study Monitoring, Day 1 of h-ATG Through Hospital Discharge

On treatment monitoring will consist of the following, unless the hospitalization is interrupted due to the participant leaving the hospital “on pass” but not to exceed more than 7 days:

- Pregnancy test (urine or blood HCG in women of child bearing potential) does not need to be repeated if done within two weeks (Day 0 to Day -14)
- CBC with differential (daily)
- Acute care, Mineral, Hepatic and Other panel (every other day)
- Reticulocyte count (weekly +/- 3 days)
- Vital signs (daily)
- CsA blood level will be monitored every week (+/- 3 days) while inpatient in the hospital and continued per section 6.3. The blood level will be monitored to ensure therapeutic range of 200 – 400 ng/ml is achieved. CsA dosage will be adjusted to target this range. More frequent drug serum levels may be obtained as needed to achieve target therapeutic levels and avoid toxicity.

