Although it is metabolized primarily in the liver, CsA major toxicity is renal. CsA causes a decrease in creatinine clearance, which almost always returns to normal range on cessation of the drug or lowering of the dose. Rare development of a hemolytic-uremic syndrome has been reported in patients with CsA after allogeneic bone marrow transplant. In our patients with SAA, frequent creatinine measurements have allowed prompt adjustment of dose and serious renal complications are infrequent.

Evidence of hepatotoxicity is common, usually as transient increases in bilirubin and transaminases. These levels often normalize with continued administration of the drug; reduction of the dose is uniformly associated with a return to normal levels.

Additional complications include hypertrichosis, gingival hypertrophy (possibly related to pre-existing poor dental hygiene), hyperesthesia, hirsutism, tremors, headaches, nausea and nonspecific gastrointestinal complaints. Hypertension may occur, and be high enough to require treatment.

Neurologic complications include insomnia, dizziness, anxiety, confusion, and vertigo. We have observed seizures in patients receiving CsA, when drug levels were within the therapeutic range. Posterior Reversible Encephalopathy Syndrome (PRES) is an increasingly recognized neurologic disorder seen in 1% of patients on cyclosporine following solid organ transplantation which manifest with acute to subacute hypertension and/or seizures.⁷⁷ In the event of hypertension, subjects will be prescribed 1 or more medications to control blood pressure in an effort to decrease the risk of this complication.⁷¹

Hypomagnesemia and hyperkalemia may occur but are asymptomatic. Increases in uric acid may occur and attacks of gout have been rarely reported. Cyclosporine therapy may be associated with a modest increase of serum triglycerides or cholesterol.

Less frequent adverse events include:

Autonomic Nervous System: dry mouth, increased sweating

Systemic: allergy, asthenia, hot flushes, malaise, weight decrease, weight increase

Cardiovascular: abnormal heart sounds, cardiac failure, myocardial infarction, peripheral ischemia

Central and Peripheral Nervous System: hypoesthesia, neuropathy, vertigo

Endocrine: goiter

Gastrointestinal: constipation, dysphagia, enanthema, eructation, esophagitis, gastric ulcer, gastritis, gastroenteritis, gingival bleeding, glossitis, peptic ulcer, salivary gland enlargement, tongue disorder, tooth disorder

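### The cyclosporine dosing paragraph for children under 12 defines obesity by the 12-to-20 age band, so read literally its obesity adjustment applies to no one

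*Combined protocol and SAP*

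**What the plan says.** Section 5.2 (Cyclosporine) has two starting-dose paragraphs.

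- **Age 12 and over:** 6 mg/kg/day in two doses. Obesity is a BMI above 35 for those over 20, and a BMI above the 95th percentile for ages 12 to 20.
- **Under 12:** "cyclosporine will be started on day 1 at 6 mg/kg/dose by mouth administered every 12 hours (total daily dose of 12 mg/kg/day". Obesity is "defined as a body mass index > 95 th percentile in subjects 12 to 20 years of age".

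Both paragraphs use actual weight by default. For obese subjects both substitute an adjusted weight halfway between ideal and actual weight. The same section then defines ideal weight for ages 2 to 20 as the "50th percentile weight based on CDC growth curves".

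Three provisions bear on the consequences:

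- **Titration:** after the start, the investigator adjusts the dose "to aim for a therapeutic trough level between 200 and 400 mcg/L" (section 5.2).
- **Prior CsA:** "In subjects who had a therapeutic CsA level established prior to protocol enrollment, the same CsA dose will be initiated" (section 5.2), so these subjects do not use the weight-based starting dose.
- **Inpatient monitoring:** section 6.2 states that "CsA blood level will be monitored every week (+/- 3 days) while inpatient in the hospital" and also lists "Acute care, Mineral, Hepatic and Other panel (every other day".

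**The concern.** The age band that is right in the paragraph for subjects 12 and over reappears in the paragraph for younger children, where it cannot be met. The exception for obese children therefore has no members, and all of them default to actual weight.

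This is an operative dosing instruction for a group the trial enrols, since eligibility starts at age 2 (section 4). It applies to the group with the higher dose per kilogram, and the error runs towards a larger dose. Section 11.4.2 names the kidney as the main site of CsA toxicity and describes signs of liver toxicity as common. Staff who notice the problem must either give a dose the authors did not intend or depart from the written rule.

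**Working it through.** **1. The stated dose.** 6 mg/kg/dose × 2 doses per day = 12 mg/kg/day, as section 5.2 states.

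**2. Who the exception covers.** The paragraph applies to ages below 12, and its obesity definition to ages 12 to 20. No age satisfies both. No other section defines obesity for children under 12.

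**3. What was intended.** The under-12 paragraph contains its own exception, its own percentile threshold and the midpoint formula. The paediatric ideal weight starts at age 2, and its range below 12 would serve no purpose if no younger child could be adjusted. The adjustment was evidently meant to apply.

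**4. Size of the dose difference.** Let A be actual weight, I ideal weight and k = A/I.

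- Literal dose = 12 × A
- Intended dose = 12 × (A + I)/2
- Ratio of literal to intended = 2A/(A + I) = 2k/(1 + k)

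The documents give no weights, so k is assumed. The last two columns also assume an ideal weight of 30 kg.

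| k | 2k/(1 + k) | Excess | mg/day per kg of midpoint weight (intended: 12) | Literal dose, mg/day | Intended dose, mg/day |
|---|---|---|---|---|---|
| 1.3 | 2.6/2.3 = 1.130 | 13% | 13.6 | 12 × 39 = 468 | 12 × 34.5 = 414 |
| 1.5 | 3.0/2.5 = 1.200 | 20% | 14.4 | 12 × 45 = 540 | 12 × 37.5 = 450 |
| 2.0 | 4.0/3.0 = 1.333 | 33% | 16.0 | 12 × 60 = 720 | 12 × 45 = 540 |

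**5. How many children.** Section 2.9.4 reports 178 of 182 accrued, before the 25 laboratory places were added.

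- *From the total:* the ceiling is 207. Cohort 2 closed at 31 of 33, which removes 2 places: 207 − 2 = 205, and 205 − 178 = 27 left.
- *From the open cohorts:* the extension cohort has 87 − 86 = 1 place, plus 25 laboratory places = 26.
- *Expected under 18,* at the roughly 20% given in section 11.1: 0.20 × 27 = 5.4, or 0.20 × 26 = 5.2.

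An affected child must also be under 12, obese and without an established CsA dose. The documents give no rates for these, but the number must be smaller than about 5 and may be zero.

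**The case against.** The best counter-argument concerns weight, not fact. The intended rule can be recovered from the section itself, because the harmful reading makes the paragraph's own exception void. A prescriber would probably apply the evident rule, and nothing in the documents shows that any child was dosed otherwise. That is fair, and it lowers the likely harm. It does not make the text right.

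One could also read the age phrase as naming the reference population for the percentile, so that a very obese younger child might still exceed it. That reading is strained, and under it the threshold would still be the wrong one for a younger child.

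The safeguards also count. Doses are titrated to a trough, and section 6.2 allows CsA levels more often than weekly when needed. Section 11.4.2 reports that in the investigators' own patients "frequent creatinine measurements have allowed prompt adjustment of dose". These measures act only after dosing has begun, so they limit an excessive start without preventing it.

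Finally, the percentages rest on assumed weight ratios, and the 33% figure needs a child at twice ideal weight. The protocol is dated March 2020 and does not give accrual at that date, so fewer places may have remained than calculated. A correction cannot alter doses already given. All of this stands, and it keeps the point minor.

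**Conclusion.** The concern holds. As written, the obesity adjustment in the under-12 paragraph cannot apply to any child that paragraph covers. The cause appears to be an age band carried over from the paragraph above.

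Taken literally, the rule starts an obese child under 12 about 13% to 33% above the intended dose, for assumed actual-to-ideal weight ratios of 1.3 to 2.0. The effect is confined to the starting dose of children with no established CsA dose. With 26 or 27 places left at the time of section 2.9.4, very few children could be affected. The primary endpoint, sample size, two-stage design and stopping rules do not depend on it. This is a low-priority editorial error, worth correcting because it sits in a paediatric dosing rule and runs towards overdosing.

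**What to change.** In the under-12 paragraph of section 5.2, replace the age band in the obesity definition with subjects aged 2 to under 12. Keep the 95th-percentile threshold, the midpoint formula and the ideal-weight definition unchanged.

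The cost is a one-phrase correction that can go into the next amendment. It needs no new clinical decision, because the threshold is already stated, and no change to the design or analysis.

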2.9.1 Justification for adding Cohort 2 (August 2013)

In this study, we are observing more rapid hematologic improvement than observed with immunosuppression alone. The overall response rate of 84% (11/13) at 6 months, with 100% of these responses observed by 3 months, is also higher than in historical data. As subjects currently receive eltrombopag for 6 months but blood counts have improved by 3 months, it is possible that administration of eltrombopag may only be necessary for the shorter duration, lowering risk, cost, and inconvenience. In particular, limiting exposure to eltrombopag may reduce the risk of cytogenetic evolution. Further, in the event of relapse, expected with discontinuation of treatment, we can now not distinguish whether cyclosporine or eltrombopag is responsible, as both are administered concurrently. Therefore, we propose to treat another cohort (cohort 2) of 31 subjects, with no change to this protocol other than a reduction in eltrombopag administration from 6 to 3 months. The study objectives, primary and secondary endpoints, statistics – sample size, stopping rules, eligibility, monitoring and ancillary studies will remain unchanged. Responses at 3 months can be assessed for the two cohorts, providing a confirmation cohort for our early results, whereas new information will be provided by comparison of long-term outcomes between the two cohorts. These data can be used to inform design of a future randomized, multicenter phase III trial. Note amendment 17 was submitted on October 23, 2014 to increase Cohort 2 sample size to 33 subjects in order to allow subjects to be enrolled and treated while amendment 16 to add Cohort 3 was being reviewed. Note, only 31 subjects were enrolled into Cohort 2 because the Cohort 3 amendment was approved prior to needing to enroll the 2 additional subjects into Cohort 2.

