5.7 Extended Access to Study Drug

Responders:

Cohorts 1 and 2: Study drug (eltrombopag) administration will be discontinued at 6 months for subjects in cohort 1 and at 3 months* for subjects in cohort 2; cyclosporine will be discontinued at 6 months for both cohorts.

Cohorts 1 and 2 Subjects that Relapse:

In cohort 2, if a subject who received eltrombopag for 3 months* has evidence of relapse as defined in Section 7, eltrombopag and/or cyclosporine can be restarted at the clinical investigator's discretion. Such cohort 2 subjects, who require treatment prior to month 6, will be denoted as non-responders at 6 months

for statistical purposes.

Subjects in cohort 1 or 2 that relapse (defined in section 7) after the end of 6-month treatment period while in follow-up may have eltrombopag and/or cyclosporine restarted at the clinical investigator's discretion. Subjects in cohort 2 that received the reduced CsA dose (2mg/kg/day) starting after the 6-month landmark visit who relapse despite the prolonged reduced dose of CsA may have the CsA dose increased to achieve therapeutic levels (trough levels 200-400) at the clinical investigator's discretion. Subjects can remain on the drugs under this protocol until the end of the 5 year follow-up period.

*Study drug (eltrombopag) administration will be discontinued at 3 months for subjects in cohort 2, except for subjects experiencing dose delays/interruptions as outlined in Section 5.3.

Cohort 3 and Extension Cohort:

Subjects that relapse (defined in section 7) after the end of 6-month treatment period while in follow-up may have eltrombopag restarted at the clinical investigator's discretion. In addition, the cyclosporine dose may be increased to achieve a therapeutic level. Subjects can remain on the drugs under this protocol until the end of the 5-year follow-up period.

Laboratory Exploratory Cohort:

Follow up for subjects in this cohort will be the same as Cohort 3 and Extension Cohort (above).

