9.2 Statistical Methods

For each cohort, the planned analyses will include descriptive statistics on the proportions of responses (% subjects with partial or complete response), cumulative incidence of response with death considered to be a competing risk and the time to complete response. The response probabilities, including complete response probability and partial response probability, will be estimated using the sample proportions, and their inferences, including confidence intervals and hypotheses testing, will be evaluated using Binomial distributions. Survival analysis will include methods based on Kaplan-Meier estimates and Cox regression. Although we have a small sample size, if it is appropriate, we will consider additional analyses for the primary and secondary endpoints using the analysis of variance, multiple regression and logistic regression models. Graphical tools will be used to display the appropriate estimates (i.e. estimated proportions and Kaplan-Meier curves) and their corresponding 95% confidence intervals.

Results for each cohort will be compared separately to the historical data from the large numbers of patients treated at the NIH previously with either a single or repeat course of immunosuppression from prior NHLBI studies: the h-ATG/CsA protocol (90-H-0146); the h-ATG/CsA vs. Cytoxin/CsA protocol (97-H-0117); the h-ATG/CsA/MMF protocol (00-H-0032); the h-ATG/CsA/Rapamune protocol (03-H-0193); the r-ATG vs. alemtuzumab protocol (03-H-0249); and h-ATG/CsA vs. r-ATG/CsA protocol (06-H-0034). More specifically, results from the current trial will be compared to our large historical experience with a horse ATG based regimen in nearly 400 patients (from the aforementioned studies) of a hematologic response rate of 60-70%, a complete response rate of 10-15%, a relapse rate of 30-40%, a clonal evolution rate (any clonal abnormality) of 15-20%, and a high risk evolution rate (to monosomy 7, high risk MDS, leukemia, or complex cytogenetics) of 10-15%.

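### Cohort 2 mixes two cyclosporine schedules after month 6, so its relapse results need to be shown by schedule before they are compared with cohort 1 or historical data

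*Combined protocol and SAP*

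**What the plan says.** Section 2.9.1 added cohort 2 "with no change to this protocol other than a reduction in eltrombopag administration from 6 to 3 months". One of its reasons was that, if relapse followed the end of treatment, "we can now not distinguish whether cyclosporine or eltrombopag is responsible, as both are administered concurrently". It adds that "new information will be provided by comparison of long-term outcomes between the two cohorts".

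Section 5.2 then reports a review of data as of 17 September 2014 in which "a trend towards a higher than expected number of relapses after the 6 month landmark visit were observed", and changes the schedule: "For remaining subjects due for the 6 month timepoint on cohort 2 we will prolong administration of cyclosporine beyond 6 months". Month-6 responders covered by the change take a fixed 2 mg/kg/day through month 24.

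Section 5.7 still says, for cohorts 1 and 2, that "cyclosporine will be discontinued at 6 months for both cohorts". A little further on it refers to those cohort-2 subjects who received the reduced dose, which implies that others did not. A design-figure footnote in section 3 attributes the change to amendment 15 and reads as if it covered all of cohort 2.

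On analysis, section 9.2 states that "Results for each cohort will be compared separately to the historical data", and gives a historical relapse rate of 30-40%. Section 9.4 lists relapse as endpoint (b), and the effect of 2.0 mg/kg/day CsA on relapse among month-6 responders as endpoint (g). Section 9.1 introduces that last objective with cohort 3. No section names CsA schedule as a stratum, covariate or censoring rule for relapse in cohort 2.

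**The concern.** Cohorts 1 and 2 were meant to differ in eltrombopag duration alone. After the change, cohort 2 as a whole also differs from cohort 1 in CsA exposure after month 6, and by an amount that depends on how many subjects had already passed month 6.

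The plan itself treats CsA schedule as relevant to relapse. The change was made to improve relapse, and section 5.2 says a longer course in earlier trials delayed relapse by a year. The event is also recorded differently. Under section 7, a subject who stopped CsA is dated as relapsed when CsA is resumed; a subject on the low dose is dated when a higher dose is needed.

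A single cohort-2 relapse rate or curve would therefore average two schedules and two event triggers. A low rate could be credited to shorter eltrombopag when longer CsA produced it, or a real cost of shorter eltrombopag could be hidden.

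**Working it through.** **The plan's own figure.** The documents give no sample size or power for relapse. The only sizing that applies to cohort 2 is the Simon two-stage design for complete response (CR) at 6 months in section 9.1: stop if 2 or fewer of 24 respond, accept the null if 6 or fewer of 31 respond. Summing P(X1 = x; n = 24) × P(X2 ≥ 7 − x; n = 7) over x = 3 to 24 gives power 0.8651 at 30% (stated: 0.865) and type I error 0.0305 at 10%. It reproduces, and it is untouched, because the endpoint is reached before the CsA change applies.

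**Split of cohort 2 (not stated; assumptions needed).**
- Inputs: 26 of 31 subjects enrolled by 15 September 2014 (section 2.9.2); cohort-2 amendment submitted 22 August 2013 (section 9.1); data review as of 17 September 2014 (section 5.2).
- Assumptions: uniform accrual; first enrolment between 22 August 2013 and 1 January 2014; the data-review date stands in for the date the change took effect. Subjects enrolled by 17 March 2014 had then passed month 6.
- Formula: 26 × (days from start to 17 March 2014) / (days from start to 15 September 2014).
- Start 22 August 2013: 26 × 207/389 = 13.8.
- Start 1 December 2013: 26 × 106/288 = 9.6.
- Start 1 January 2014: 26 × 75/257 = 7.6.

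So about 8 to 14 of 31 had passed month 6, leaving 17 to 23 (55% to 74%) for the longer schedule. These are enrolled subjects. Only responders continue CsA or can relapse, so both groups are smaller in the analysis. The effective date of amendment 15 is not given; a later date would enlarge the group that stopped.

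**Size of the bias.** Let R be relapse with CsA stopped, m the share of cohort-2 responders on 2 mg/kg/day, and RR the assumed relative risk of relapse on low-dose CsA by the analysis time. With no effect of eltrombopag duration, cohort 2 shows R × (m × RR + 1 − m). Take R = 35%, the middle of the plan's 30-40%.

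| RR | m = 50% | m = 80% | Spurious difference from 35% |
|---|---|---|---|
| 1.0 | 35% | 35% | none |
| 0.75 | 30.6% | 28.0% | 4.4 to 7.0 points |
| 0.5 | 26.3% | 21.0% | 8.8 to 14.0 points |

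Masking: if shorter eltrombopag truly raised relapse 1.5-fold, to 52.5%, and RR were 0.5, cohort 2 would show 52.5% × 0.75 = 39.4% (m = 50%) or 52.5% × 0.60 = 31.5% (m = 80%), against 35% in cohort 1.

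**Precision of the unmixed contrast.** The 84% response rate in section 2.9.1 gives 0.84 × 31 ≈ 26 responders per cohort. The half-width of the 95% interval for a difference, at 35% in both groups, is 1.96 × √(0.2275/26 + 0.2275/n).
- All of cohort 2, n = 26: ±26 points.
- Only those assigned to stop, n = 13 or 10: ±32 or ±35 points.
- Applying 84% to the 8 to 14 above gives n of about 7 to 12: ±40 to ±33 points.

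**The case against.** The strongest reply is that little is lost. Section 3 describes a non-randomised pilot with sequential cohorts, so cohort 1 against cohort 2 could never isolate the effect of eltrombopag duration, and no formal relapse test between them is planned. The comparison comes from the August 2013 rationale, written before the CsA change. All of this is correct, and it is why the result should be labelled descriptive. It does not remove the problem: the comparison is still a stated purpose of cohort 2, and the CsA change adds a known difference that can be separated out.

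A reader might infer that cohort 2 can no longer serve its purpose. The documents do not support that. Section 2.9.1 also cites lower risk, cost and inconvenience, possibly less cytogenetic evolution, and a confirmation cohort for 3-month response. Because eltrombopag stops at 3 months and CsA not before 6, the interval between shows eltrombopag withdrawal on the original CsA schedule. Section 2.9.2 already reports that counts were maintained or normalised over it.

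A reader might also infer that every planned analysis is fixed at cohort level. The by-cohort sentence that opens section 9.2 lists response analyses only; relapse enters through the historical comparison. Endpoint (g) is defined by CsA exposure, and section 9.2 allows Cox and other regression models. But (g) states neither population nor comparator, and no covariates are named, so the mixture is left unresolved.

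Finally, section 5.2 says that in earlier trials a gradual taper left the relapse rate unchanged and a longer course only delayed relapse. That counts against assuming a lasting reduction and points to a bias that depends on follow-up time.

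**Conclusion.** The concern holds for relapse after month 6. Reported for cohort 2 as a whole, it is confounded by CsA schedule in any comparison with cohort 1 or with the historical 30-40%. Three-month response, 6-month CR and outcomes between months 3 and 6 are not affected.

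The split of roughly 8 to 14 against 17 to 23 enrolled subjects rests on assumed uniform accrual, start date and switch date. The bias rests on an assumed CsA effect: none at a relative risk of 1.0, about 4 to 7 points at 0.75, and about 9 to 14 points at 0.5 with 50-80% of the cohort on the low dose. The documents establish neither its size nor its direction. If CsA mainly delays relapse, the distortion would be greatest in time-to-relapse curves and in rates read up to about month 24.

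**What to change.** In sections 9.2 and 9.4:

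1. Report cohort-2 relapse among month-6 responders separately by assigned CsA schedule, defined by whether the month-6 visit fell before or after the CsA amendment took effect. Use assignment, not achieved exposure: section 5.2 keeps CsA interruptions in the medical record only.
2. Show time-to-relapse curves for each group, and note that the trigger in section 7 differs by schedule.
3. Limit the eltrombopag-duration comparison with cohort 1 to cohort-2 responders assigned to stop CsA at month 6, and label it descriptive.
4. For endpoint (g), state the population and show late cohort 2, cohort 3 and the extension cohort separately. Pooling late cohort 2 with cohort 3 would mix day 14 to 3 months of eltrombopag with day 1 to 6 months. Section 9.1 includes the extension cohort in secondary endpoints, so it should not be left out.
5. Reconcile the section 3 footnote, section 5.2 and section 5.7 on which cohort-2 subjects continued CsA, and give the number on each schedule.

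The cost is analysis wording and smaller groups: about ±32 to 35 points instead of ±26 with 10 to 13 responders assigned to stop, and up to about ±40 with 7. No change to treatment is involved.
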